2.8.4 Other safety data

2.8.4.1 ECG and cardiac imaging data

A standard 12-lead ECG will be performed at screening to assess the eligibility of subjects. No analysis will be done for ECG measurements.

2.8.4.2 Vital signs

Analysis in vital sign measurement using descriptive summary statistics for the change from baseline for each post-baseline visit will be performed by vital sign and treatment group. Change from baseline will only be summarized for subjects with both baseline and post-baseline values and will be calculated as:

$$\text{change from baseline} = \text{post-baseline value} - \text{baseline value}$$

Only “on-treatment” vital signs will be summarized (i.e. assessments within last dose plus 84 days). All vital signs will be listed with “on-treatment” flag displayed.

The number and percentage of subjects with newly occurring notable vital signs abnormalities will be presented. Criteria for notable vital sign abnormalities are provided in [Table 2-11](#) below. A listing of subjects with newly occurring notably abnormal vital signs will be provided.

Table 2-11 Criteria for notable vital sign abnormalities

Vital sign (unit)	Notable abnormalities
Systolic blood pressure (mmHg)	$\geq 140 \text{ mmHg}$ or $< 90 \text{ mmHg}$
Diastolic blood pressure (mmHg)	$>90 \text{ mmHg}$ or $<60 \text{ mmHg}$
Pulse (bpm)	$> 100 \text{ bpm}$ or $<60 \text{ bpm}$

[REDACTED]

2.11 Clinician-reported outcomes

2.11.1 Usability and hazard assessment of the 2 mL auto-injector

This analysis will be based on the Safety Set.

The number and percentage of subjects who successfully completed each and ALL of the indicated steps as per the IFU will be summarized by visit and treatment group, including total.

The number and percentage of subjects who experienced each and ANY of the defined possible hazards will be summarized by visit and treatment group, including total.

Successful self-injection will be positively defined for a subject when the subject performs the six critical steps as per the IFU (i.e. P7, P9, P10 and P11). Number and percentage of subjects who passed the self-injection successfully as well as a two-sided 95% exact confidence interval at Week 1 visit will be summarized by visit and treatment group, including total. The following statistical hypothesis will be tested by an exact binomial test at one-sided 2.5% level of significance at Week 1 visit:

H_0 : successful auto-injector use rate $< 90\%$

H_1 : successful auto-injector use rate $\geq 90\%$

Missing values with respect to the self-assessment checklist and possible hazard assessment checklist will not be imputed while summarizing the answers of each question with frequencies.

Subjects with one or more of the critical steps missing will be considered as unsuccessful (imputation with non-response) with regard to the self-injection success. Subjects who discontinued or who missed a visit and have the full self-injection checklist missing will not be evaluated with regard to the self-injection success at the corresponding visit.

Visit windows will not be applied to self-injection assessment and possible hazard assessment. The analysis visit will refer to the visit as per the CRF.

Of note: only data in the self-assessment checklist with self-injection checked in eCRF Dosage Administration Record (DAR) page are included in the analyses.

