P2	Cleaned the injection site	No
P3	Removed the auto-injector from the outer box	No
P4	Checked expiration date on auto-injector label	No
P5	Inspected the auto-injector for damage	No
P6	Inspected liquid for brown discoloration or particles	No
P7	Removed cap from auto-injector	Yes
P8	Discarded cap	No
P9	Hold the auto-injector at correct angle to the injection site	Yes
P10	Press the auto-injector firmly against the skin to trigger the injection (1 st Click), and keep holding the auto-injector firmly against the skin	Yes
P11	Wait until the injection is complete, confirmed by the 2 nd "click" and/or a check that the yellow indicator fills the window	Yes
P12	The auto-injector can now be removed	No
P13	Check again that the yellow indicator fills the window	No
P14	Disposed used auto-injector in a sharps container	No

Table 8-6 Possible hazard assessment check list (auto-injector)

No.	Possible Use-related hazards
H1	Was there a needle stick in a critical area (eg, eye, carotid artery)?
H2	Was there a needle stick in a non-critical area ¹ ?
H3	Was any part of the device swallowed? If yes, please specify.
H4	Was an immediate type allergic reaction noticed to device material?
H5	Was increased pain noticed by the patient due to bent needle?
H6	Was there breakage of the device observed? ²
H7	Was swallowing of material debris observed?
H8	Was any other problem observed? ³
H9	Was less than the full dose administered? ⁴

The following potential hazards from the Hazards Identified List ([AIN457_HID_Delta225-01]) have not been included as not being observable during self-injection observation: microbiological contamination, wrong drug, transfer of transmissible diseases.

¹ Excluding the actual injection into the appropriate injection site of the body

²If yes, then it is to be specified under which circumstances breakage occurred and which parts were affected, as well any additional problems (eg, injuries) due to the breakage are to be described.

³If yes, then it is to be specified. Possible events might include: irritated skin; drug too cold when injected; the drug or device upon visual inspection appeared unsuitable for injection; intradermal instead of subcutaneous injection; and other events.

⁴If yes, then it is to be specified why, eg, leakage from injection site, early removal.

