This consist of the assessment of successful 2mL AI **self-administration by the subject** at Visit Week 1, by studying the number and percentage of subjects who successfully perform this self-injection (note: **without** prior explanations/instructions at this visit, as this has been performed prior to dosing at Randomization only). Successful self-injection is achieved when the subject performs all required steps effectively and safely to deliver the correct dose from the device at the correct injection site. The sequence of user steps as per IFU “required to be completed for successful administration” are identified in [Table 8-5](#), these 4 critical steps will be used to define successful administration. The general passing usability goal for ‘successful use’ task completion will be defined as $\geq 90\%$ pass rate of following these steps.

Secondary usability assessment:

- This consist of the assessment of 2mL AI **subject use errors** that occur during the First Use at Randomization (after providing initial explanations/instructions) and repeated self-injection at Visit Week 1 (without a detailed explanation/instruction on handling the new form) by investigating the frequency of observed or reported difficulties in completing the 2mL AI self-injection after initial explanations/instructions and self-injection without explanations/instructions after a time lag that represents standard treatment. The number and percentage of subjects who successfully complete each of the indicated steps as per the IFU ([Table 8-5](#) self-injection assessment check list) as well as the number and percentage of subjects who experience any of the defined possible hazards (based on identified hazards list) as well as non-directed querying for any observed problems during self-injection ([Table 8-6](#)) will be computed by visit.
- This consist of the assessment of successful First Use by subject after initial explanations/instructions, by studying the number and percentage of subjects at Randomization who successfully perform the self-injection as defined above for the primary usability assessment.

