5.6 Clinician reported outcomes

5.6.1 Usability and hazard assessment of the 2 mL auto-injector

The goal is to measure and evaluate the usability of the auto-injector during observed use. During the first 2mL self-injection at the respective visits (Randomization and Week 1), site staff will observe and complete the self-injection assessment checklist ([Table 5-2](#)) to assess the ability to follow the instructions for use (IFU). The possible hazard checklist ([Table 5-3](#)) will be assessed for the 2mL self-injection at each of the two visits.

Primary usability assessment:

- Assessment of successful self-administration by the subject at Week 1. Successful self-injection is achieved when the subject performs all required steps effectively and safely to deliver the correct dose from the device at the correct injection site. The sequence of user steps (as per IFU) that are minimally required are P7, P9, P10 and P11 ([Table 5-2](#)), these 6 critical steps will be used to define successful administration. The general passing usability goal for ‘successful use’ task completion will be defined as $\geq 90\%$ pass rate following these steps.

Secondary usability assessment:

- Assessment of subject use errors that occur during the First Use at Randomization (after initial training) and repeated self-injection at Week 1 (without retraining).
- Assessment of successful First Use by subject after initial training (at Randomization), for subjects who successfully perform the self-injection as defined above for the primary usability assessment (i.e. P7, P9, P10 and P11).

Table 5-2 Self injection assessment checklist (auto-injector)

No.	IFU indicated steps	Required to be completed for successful administration
P1	Washed hands with soap and water	No
P2	Cleaned the injection site	No
P3	Removed the auto-injector from the outer box	No
P4	Checked expiration date on auto-injector label	No
P5	Inspected the auto-injector for damage	No
P6	Inspected liquid for brown discoloration or particles	No
P7	Removed cap from auto-injector	Yes
P8	Discarded cap	No
P9	Hold the auto-injector at correct angle to the injection site	Yes
P10	Press the auto-injector firmly against the skin to trigger the injection (1 st Click), and keep holding the auto-injector firmly against the skin	Yes
P11	Wait until the injection is complete, confirmed by the 2 nd “click” and/or a check that the yellow indicator fills the window	Yes

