No.	IFU indicated steps	Required to be completed for successful administration
P12	The auto-injector can now be removed	No
P13	Check again that the yellow indicator fills the window	No
P14	Disposed used auto-injector in a sharps container	No

Table 5-3 Possible hazard assessment checklist

No.	Possible hazard assessment checklist
H1	Was there a needle stick in a critical area (e.g. eye, carotid artery)?
H2	Was there a needle stick in a non-critical area? ¹
H3	Was any part of the device swallowed? If yes, please specify.
H4	Was an immediate-type allergic reaction noticed to device material?
H5	Was increased pain noticed by the patient due to a bent needle?
H6	Was the breakage of the device observed? ²
H7	Was swallowing of material debris observed?
H8	Was any other problem observed? ³
H9	Was less than the full dose administered? ⁴

The following potential hazards from the Hazards Identified List ([AIN457_HID_Delta225-01]) have not been included as not being observable during self-injection observation: microbiological contamination, wrong drug, transfer of transmissible diseases.

¹ Excluding the actual injection into the appropriate injection site of the body

² If yes, then it is to be specified under which circumstances breakage occurred and which parts were affected, as well any additional problems (e.g. injuries) due to the breakage are to be described.

³ If yes, then it is to be specified. Possible events might include: irritated skin; drug too cold when injected; the drug or device upon visual inspection appeared unsuitable for injection; intradermal instead of subcutaneous injection; and other events.

⁴ If yes, then it is to be specified why, e.g. leakage from injection site, early removal.

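### The Week 1 auto-injector success variable omits the partial-dose item H9, so a subject with all four critical steps ticked but an incomplete dose on record counts as a success

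*SAP*

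**What the plan says.** Protocol 8.5.1, under the primary usability assessment, first describes the aim: "Successful self-injection is achieved when the subject performs all required steps effectively and safely to deliver the correct dose from the device", and at the right site. The same paragraph then refers to Table 8-5 and states that "these 4 critical steps will be used to define successful administration". Table 8-5 marks four of its 14 steps as required:

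- P7: cap off
- P9: correct angle
- P10: press to trigger and keep pressing
- P11: "Wait until the injection is complete", shown by the second click and/or the yellow indicator

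Step P13, "Check again that the yellow indicator fills the window", is not required.

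SAP 5.6.1 repeats the description and names the same four steps, although it says "these 6 critical steps will be used to define successful administration". SAP 2.11.1 grants success "when the subject performs the six critical steps as per the IFU (i.e. P7, P9, P10 and P11". It reports the Week 1 rate with an exact two-sided 95% interval and tests it against 90%. A subject with any critical step missing is unsuccessful; a subject with the whole checklist missing is not evaluated.

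The observer also completes a hazard checklist for the same injection. Item H9 asks "Was less than the full dose administered", and its footnote adds: "If yes, then it is to be specified why, e.g. leakage from injection site, early removal". SAP 2.11.1 tabulates each hazard and any hazard by visit and treatment group. No hazard item enters the success variable.

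**The concern.** The described outcome is a delivered dose, but the analysed outcome is four handling steps. When the two disagree, the trial holds a direct record of the disagreement in H9 and does not use it for the rate, the interval or the test.

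The rule is also uneven in strictness. An unrecorded critical step makes a subject a failure, while a recorded partial dose need not.

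At stake is the primary usability result for a device meant to give 300 mg in a single injection, in a study intended to support its registration. The rate could be declared to exceed 90% while a separate table shows that some of the counted successes did not deliver the full dose.

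**Working it through.** **Step 1. Where the rule and the description part.**

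| P7, P9, P10, P11 | H9 | Counted as | Correct-dose description |
|---|---|---|---|
| all yes | no | success | met |
| all yes | yes | success | not met |
| any no | yes or no | failure | not met (a required step was not done) |

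Only the second row is a problem. Of the two causes named in the H9 footnote, early removal breaks the hold in P10 or the wait in P11, so it should normally fall in the third row. Leakage can follow a completed device cycle and leave all four steps ticked. P11 may also be ticked on the click alone, and the later indicator check (P13) is optional, so P11 = yes with H9 = yes is possible. Neither document has a rule for that combination.

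**Step 2. Direction.** Subjects with four steps done and H9 = no are a subset of those with four steps done. The four-step rate is therefore never below the dose-complete rate. Each second-row subject adds 1/120 = 0.8 points (pooled) or 1/40 = 2.5 points (one arm of 40).

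**Step 3. Inputs for the test.** The null rate is 0.90 and one-sided alpha is 0.025 (SAP 2.11.1). Total N is about 120, randomized 2:2:1:1, so 120 × 2/6 = 40 in each full-size arm. Every arm injects an active or placebo 2 mL auto-injector, so all 120 can contribute. The SAP summarises by treatment group including total, but does not say to which the test applies. The plan gives no sample size, power or minimum count for this test, so there is no stated figure to reproduce.

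**Step 4. Thresholds.** p(r) = P(X ≥ r) = sum over k = r to n of C(n,k) × 0.9^k × 0.1^(n−k).

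For n = 40: p(40) = 0.9^40 = 0.0148, and p(39) = 0.0148 + 40 × 0.9^39 × 0.1 = 0.0805.

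| n | successes | rate | p | exact 95% interval |
|---|---|---|---|---|
| 120 | 115 | 95.8% | 0.0160 | 90.5% to 98.6% |
| 120 | 114 | 95.0% | 0.0382 | 89.4% to 98.1% |
| 40 | 40 | 100% | 0.0148 | 91.2% to 100% |
| 40 | 39 | 97.5% | 0.0805 | 86.8% to 99.9% |

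The pooled test allows five failures and the 40-subject test allows none. Fewer evaluable subjects give the same picture: 109 of 114 passes (p = 0.0239) and 108 does not (p = 0.0544); 36 of 36 is needed at n = 36 (p = 0.0225).

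**Step 5. Illustration under assumed rates.** Let s be the true four-step rate and h the share of four-step passers with H9 = yes. Neither is in the documents. With H9 required, the success probability is s × (1 − h). Chance of reaching 115 of 120:

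| s | h = 0 | 1% | 2% | 3% | 5% |
|---|---|---|---|---|---|
| 97% | 84.7% | 65.8% | 45.4% | 28.1% | 8.4% |
| 98% | 96.6% | 85.0% | 66.0% | 45.4% | 15.7% |
| 99% | 99.9% | 96.7% | 85.0% | 65.8% | 27.5% |

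The h = 0 column is also the chance of passing under the planned four-step rule, whatever h is.

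**The case against.** The strongest reply is that the SAP does what the protocol says. Protocol 8.5.1 adopts the four-step rule in the same paragraph as the description, and Table 8-5 marks the steps that success requires. A reader might infer that the SAP departs from the protocol; it does not. The mismatch between description and rule is in both documents.

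Three more replies have force:

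- **P10 and P11 bear on dose completion.** A reader might infer that any partial dose counts as a success. The documents do not support that, because early removal should normally fail one of these steps.
- **H9 is not ignored.** It is tabulated by visit, its cause is recorded, and the protocol has observed problems analysed case by case.
- **The construct is arguable.** The objective separates following the instructions from use-related hazards, and leakage after correct handling can be seen as a hazard. The description also mentions safety and injection site, and the other hazard items are not in the rule either.

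It is also true that one reclassification at the boundary flips any exact test, and that the H9 rates above are assumed.

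What these replies leave open is the combination of four steps ticked and H9 = yes. H9 is the one hazard item that directly contradicts the dose part of the description. Reporting it in another table does not change the tested rate.

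**Conclusion.** The point holds in a limited form. A subject with P7, P9, P10 and P11 all yes and H9 also yes is counted as a success in the Week 1 rate, interval and test, contrary to the description of success in both documents. The effect runs only in the device's favour. One such subject is enough to change the result at 115 versus 114 of 120, or at 40 versus 39 of 40. Those thresholds rest on about 120 subjects, all evaluable, and on which population is tested. How often the combination occurs cannot be known from the documents.

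Two stronger readings should be resisted. A reader might take dose delivery to be the trial's main question. The primary objective is PASI 75 and IGA 0 or 1 against placebo; usability is an other-secondary objective outside the H1 to H3 sequence, so the efficacy conclusion does not move. A reader might also infer from the count of six that two conditions were dropped. The SAP names four steps and the protocol says four, so this is a wording slip that leaves the derivation unchanged.

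**What to change.** In SAP 2.11.1 and 5.6.1, count a subject as a success only if P7, P9, P10 and P11 are yes and H9 is no. Use this for the Week 1 rate, interval and test, and for First Use at Randomization. State how a missing H9 is handled, for example as unsuccessful, in line with a missing critical step. Show the protocol's four-step rate alongside.

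If the four-step rule is kept, the minimum is a pre-specified sensitivity analysis of the Week 1 rate and test counting H9 = yes as failure, with a cross-tabulation of P11 by H9.

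Either list the change in SAP section 4 or align Protocol 8.5.1; otherwise the two documents would disagree. Correct the count of six to four in both SAP places. The same edit should state whether the test applies to the total or to each arm.

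The cost is some wording and one extra condition in the derivation. No new data are needed, since H9 is already recorded at the same injection. The success rate may come out slightly lower.

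### The DAR-page filter in SAP 2.11.1 could drop Week 1 auto-injector attempts stopped for a use error from the usability denominator (minor)

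*SAP*

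**What the plan says.** **Endpoint and goal.** Protocol 8.5.1 makes successful 2 mL AI self-injection at Week 1 its primary usability assessment, studied "by studying the number and percentage of subjects who successfully perform this self-injection". A subject succeeds who "performs all required steps effectively and safely to deliver the correct dose from the device" at the correct site. Table 8-5 marks four steps as required (P7, P9, P10, P11). The goal is at least a 90% "pass rate of following these steps". SAP 5.6.1 repeats it as a 90% "pass rate following these steps".

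**Test.** SAP 2.11.1 adds a formal comparison with the same 90%: "The following statistical hypothesis will be tested by an exact binomial test at one-sided 2.5% level of significance at Week 1 visit". It also reports counts, percentages and "a two-sided 95% exact confidence interval at Week 1 visit will be summarized by visit and treatment group, including total".

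**Who is counted.** SAP 2.11.1 uses the Safety Set. A subject with any critical step missing is unsuccessful. A subject who discontinued or missed the visit, with the whole checklist missing, is not evaluated. Finally, "only data in the self-assessment checklist with self-injection checked in eCRF Dosage Administration Record (DAR) page are included in the analyses".

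**Stopped attempts.** Protocol 8.5.1 tells the observing staff member to intervene in two situations. Under (a), a use error that could harm the subject, the observer either corrects the subject and lets the injection go on, or ends it; the error is documented. Under (b), any apparent health and safety risk to anyone, the injection will probably be ended.

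**The concern.** The missing-step rule and the DAR rule can pull in opposite directions for the same event. Week 1 doses are self-administered on site under one-to-one observation (Protocol 6.1.3 and 6.7.2). A Week 1 checklist without self-injection checked is therefore likely to belong to an attempt that failed or was taken over, although a data-entry slip is also possible. Excluding that checklist would remove a use failure from an endpoint that exists to count use failures.

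What is at stake is the reported success rate for the new device, and the test of it against 90%. Protocol 4.1 says the study's data will support registration of the 2 mL auto-injector.

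**Working it through.** The plan gives no sample size, power or critical value for this test, so there is no stated figure to reproduce.

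**Inputs**
- Threshold 90%, exact binomial, one-sided 2.5% (SAP 2.11.1).
- About 120 subjects, randomised 2:2:1:1 (SAP 1.1). Every arm injects one 2 mL AI, active or placebo (Protocol 6.1.3). I assume all 120 are evaluable and pooled.
- Number of attempts stopped for a use error, and how they are entered on the DAR page: not given. The counts below are examples.

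**Step 1: follow one attempt stopped for a use error**
- Self-injection checked: the unfinished critical step is recorded as not performed, or is missing. Either way the attempt is unsuccessful and stays in.
- Self-injection not checked: the checklist is excluded before the missing-step rule applies. The failure leaves both the count and the denominator.

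**Step 2: critical values**

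p(k, n) = sum over j = k to n of C(n, j) × 0.9^j × 0.1^(n−j); reject when p ≤ 0.025.
- n = 120: p(115) = 0.0160, p(114) = 0.0382. At most 120 − 115 = 5 failures are allowed.
- n = 119: p(114) = 0.0172, p(113) = 0.0406. At most 5.
- n = 118: p(113) = 0.0183, p(112) = 0.0431. At most 5.

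The limit stays at five failures for every n from 114 to 120. Removing failures therefore moves the result directly towards rejection.

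**Step 3: drop failures**

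| All attempts | Failures dropped | Analysed | p | Result |
|---|---|---|---|---|
| 114/120 (95.0%) | 0 | 114/120 | 0.0382 | not rejected |
| 114/120 | 1 | 114/119 (95.8%) | 0.0172 | rejected |
| 113/120 (94.2%) | 0 | 113/120 | 0.0784 | not rejected |
| 113/120 | 1 | 113/119 (95.0%) | 0.0406 | not rejected |
| 113/120 | 2 | 113/118 (95.8%) | 0.0183 | rejected |

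The observed-rate goal can move too. 107/120 = 89.2% misses 90%; with two failures dropped, 107/118 = 90.7% meets it. With one dropped, 107/119 = 89.9% still misses.

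**Step 4: drop successes instead**

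An unchecked box on a successful injection lowers the rate, but hardly. 115/120 = 95.83% becomes 114/119 = 95.80%, and p goes from 0.0160 to 0.0172. With five failures, even six dropped successes leave 109/114 (p = 0.0239), still rejected. By contrast, one dropped failure adds 0.8 percentage points (95.0% to 95.8%).

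**Step 5: the goal beside the test**
- Read as an observed rate, the goal needs 0.9 × 120 = 108. The test needs 115. They differ at 108 to 114.
- Exact 95% limits: 108/120, 83.2% to 94.7%; lower limit 89.4% at 114/120 and 90.5% at 115/120.
- Chance of landing in that range: 55%, 35% and 15% at assumed true rates of 95%, 96% and 97%. It is 76% at 92% and 3% at 98%, so it depends heavily on the assumed rate.
- In a single group of 40, only 40/40 rejects (0.9^40 = 0.0148; 39/40 gives 0.0805).

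**The case against.** **The filter has a proper purpose.** The endpoint is self-administration by the subject, so a dose given throughout by someone else does not belong in it. This stands. It supports a filter on who started the injection, not on a box that may reflect how the injection ended.

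**The loss depends on a form we cannot see.** This also stands. If sites check self-injection for every attempt the subject began, nothing is lost. A reader might infer that the plan does remove failures; the documents show only that it could.

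**The event stays visible.** Use errors are documented, and hazard items H8 and H9 can record an aborted or partial dose. True, but an excluded attempt would still not count in the success rate.

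**Not every stopped attempt is a use failure.** Under Protocol 8.5.1(b) an injection may be ended for a safety risk unrelated to handling. This stands, and it rules out simply scoring all terminated attempts as failures.

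**A stronger reading about the goal and the test.** A reader might infer from the range 108 to 114 that the plan holds two contradictory pass rules. The text does not support that. SAP 2.1 bases hypothesis testing on one-sided p-values at 2.5%, the test uses the goal's own 90%, and neither document says outright that the goal is a point-estimate rule. The natural reading is that the test formalises the goal. Any observed-rate threshold differs in this way from a test against the same value. The test is also the stricter of the two, so adding it creates no false pass, and the count, percentage and exact interval are reported regardless. Likewise, because results are shown for each group and in total and every arm uses the AI, the total is the natural tested group. One sentence in the SAP would settle each of these.

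**Conclusion.** The concern holds as a conditional, minor point. As worded, the DAR restriction can override the SAP's own rule that an incomplete critical step is unsuccessful. If attempts stopped for a use error are not entered as self-injections, the Week 1 success rate is biased upward. With 120 evaluable and pooled, one such attempt among six failures changes the test result (p = 0.038 to 0.017) and raises the rate by 0.8 percentage points. The frequency is unknown, and the change of result needs a count near the critical value.

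Severity is minor: Protocol Table 2-1 places usability among the other secondary objectives, outside H1 to H3. A reader might infer that registration turns on this result, but no passage makes it do so; Protocol 4.1 speaks of the study's data as a whole.

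Four clarifications change no result in themselves: the role of the test relative to the goal, the tested group, the absence of the added test from SAP Section 4 (which lists only removals), and the step count. On the last, SAP 5.6.1 says "these 6 critical steps will be used to define successful administration" and SAP 2.11.1 also says six, yet both list four by number, so the definition is not in doubt.

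**What to change.** In SAP 2.11.1:
1. Take as denominator all Safety Set subjects who started a 2 mL AI self-injection at Week 1.
2. Count as unsuccessful any attempt terminated for a use error, completed by someone else, or not completed by the subject, whatever the DAR entry.
3. List separately attempts stopped for reasons unrelated to device use.
4. Give the DAR-restricted set as a sensitivity analysis.

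As clarifications, state whether the exact test is the formal assessment of the 90% goal or is supportive; name the total as the tested group; list the added test in SAP Section 4; and change six and 6 to four in SAP 2.11.1 and 5.6.1.

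The cost is SAP wording and one extra table. The reported success rate may be slightly lower.
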